#### Medications of interest:

Medicines of interest will be identified based on ATC 5th and 4th level codes. Some ATC codes incorporate attributes that are not immediately visible (e.g. route, indication, mechanism of action, dosage and combinations). Therefore, not every ATC code containing the name of a drug ingredient is automatically the correct classifier for that drug (i.e. some ingredients show up in more than one ATC code). As an example, medroxyprogesterone is the ingredient of 9 ATC concepts that have the same name but different attributes, such as different indications like those relevant to this study as well as the treatment of neoplastic diseases. In prior vocabulary versions, ATC 5th level concepts were mapped to RxNorm ingredients and, therefore, all those additional attributes were not considered. Although recent efforts have improved the hierarchical structure, some inconsistencies between ATC-RxNorm mapping still exit, especially for combination drugs.(25)

The use of medicines of interest will be derived from prescription data, and therefore assumptions about the use and duration of the drug will be unavoidable (e.g. drug prescriptions do not imply the actual

Authors: [name], [name], [name], [name], [name]

Version: V4.0

Dissemination level: Public

consumption of the medication). In addition, the actual reason for the prescription of the drug is not available in the data and will be assessed using age as a proxy. Age 50 will be used as a threshold to reflect indication, with women older than this age assumed to take this medication for HRT and younger women assumed to take it for non-HRT reasons. This could lead to misclassification, particularly in women who near this threshold age. Misclassification can also occur among women who experience primary ovarian insufficiency (age < 40 years) or early menopause (age 40 to 45), which are estimated to affect 1 to 3% and 5 to 10% of females of high-income countries, respectively.(26)

When assessing the line of treatment (Objective 4), treatment lines will be considered under the assumption that patients receive the treatments of interest for the same indication over time. However, this may not always be accurate, as these treatments can have multiple indications, and patients may be prescribed these medications for different purposes over time.

The cumulative dose and line of treatment for products containing NOMAC or CMA will be assessed based on exposures recorded during the study period. This assessment will ensure the quality of the data being used, as data collected before 2010 might be inconsistently reported in some data patterns. While this could lead to an underestimation of the cumulative dose or an inaccurate assessment of the line of treatment, we believe this will have a very limited impact on the study, given that we will cover over 12 years of follow-up.

#### Analysis:

Due to the limited number of feasibility counts for meningioma (in the order of hundreds across most databases), studying the effect of the restrictions of use among this population will not be feasible. A subgroup analysis for this population has been included for Objective 1 for descriptive purposes; however, it is unlikely to have a sufficient number of patients to allow for formal analysis.

The dates of the interventions were determined based on EU-level restrictions. However, we excluded the restrictions imposed in 2020 on products containing NOMAC in combination with oestradiol (see the introduction for further details). The rationale for this exclusion is that the 2020 intervention is likely to have been affected by the coronavirus disease (COVID-19) pandemic. Including this restriction could result in biased estimates, as any observed effects might be attributed to the pandemic rather than the intervention itself. The effect of the COVID-19 pandemic might still be seen in 2021, which will affect the ability to capture stable trends for Objective 6. Methodological considerations for Objective 6 will be thoroughly evaluated based on the visual assessment of the trends. Regarding the timing of interventions, some countries may have implemented national-level measures prior to the EU restrictions. These measures fall outside the scope of this study and will be considered for context and interpretation only.

The amount of current available data might not fully capture the long-term effects resulting from the RMM implemented in November 2022. Further studies using additional follow-up data (once available) might be needed to assess the long-term impact of the intervention.

Segmented regression (Objective 6) might not be appropriate if trends cannot be transformed to be linear or if there is residual autocorrelation. Other modelling approaches such as Autoregressive Integrated Moving Average (ARIMA) models could be considered. However, these methods require a substantial number of time points before and after the intervention and are not feasible given the currently available post-intervention data.

Authors: [name], [name], [name], [name], [name]

Version: V4.0

Dissemination level: Public

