#### 8.6.3 Other covariates

#### Time of the intervention:

Restrictions for NOMAC were first introduced in 2018, with a transition period from October 2018 to January 2019. Additional EU-level restrictions were implemented in 2020 for products with NOMAC in combination with oestradiol, which were not considered for the study (see limitations for further details).

Regarding the restrictions implemented in 2022, a transition period of three months (November 2022 to January 2023) will be considered to reflect the period during which the intervention was being implemented. This transition period will be applied for all pre- and post-intervention comparisons. For objectives 1 to 5, treatments initiated during this period will be considered for the overall results but not for the stratification by time period (see "Covariates for stratification" below for more information). For objective 6, aggregate monthly figures of this time period will be excluded.

Relevant dates related to the implementation of restrictions in 2018 and 2022 are detailed in Appendix II.

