#### **Covariates for stratification:**

Covariates for stratification will vary across objectives and will include:

- Age group:
   10-17, 18-34, 35-49, 50-64, +65 years.
- Indication:

Non-HRT vs. HRT. Indication will be assessed using age as a proxy (non-HRT in women aged 10-49 years, HRT in women aged >50 years).

- Dose:
  - High- vs low- dose, for NOMAC or CMA only. For NOMAC, high doses will include amounts from 3.75mg to 5mg. For CMA, high doses will include amounts from 5mg to 10mg. Low doses will be any amounts less than those specified.
- WHO 5th ATC level codes:
  - For NOMAC or CMA only, if counts allow. For NOMAC codes included will be: G03AA14, G03DB04, G03FB12. For CMA, codes included will be: G03AA15, G03AB07, G03DB06, G03FB03.
- Time period:
  - Preintervention: from start date to October 2022; Postintervention: from February 2023 to study end.

See below which covariates apply according to each objective.

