#### Objective 6:

The impact of the restrictions of use will be estimated using an ITS. This analysis will be restricted to NOMAC and CMA (assessed separately) and will be informed by results of the main analysis obtained as part of objective 1 (no meningioma restriction). For NOMAC, the intervention taken place in 2018 will also be assessed.

Time series will be assessed using segmented regression. Monthly incident counts of patients prescribed with NOMAC or CMA will be modelled using a Poisson regression model. Quasi-Poisson models will be considered in the presence of overdispersion. The effect size of the intervention will be estimated using risk ratios (RR).

The assumption of linearity will be assessed by visually inspecting the data and residuals, as well as through statistical goodness-of-fit tests. Autocorrelation will be assessed by examining the plot of residuals and the partial autocorrelation function and conducting statistical tests where possible. If seasonality is detected, it will be controlled for by including variables representing them in the regression model. If the trends are not (or cannot be transformed to be linear) or in the presence of residual autocorrelation, ITS will not be conducted due to the complexity of predicting the counterfactual and to disentangle the intervention effects.(23)

Authors: [name], [name], [name], [name], [name]

Version: V4.0

Dissemination level: Public

The impact model of the intervention (i.e. how we expect the intervention has impacted the outcome) is anticipated to show an abrupt change in the level and a gradual change in the gradient of the trend (step and slope change). Potential impact models will be further discussed and agreed with EMA and defined a priori.(23, 24)

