The amount of pre-intervention data to include for this analysis will be based on defining a valid counterfactual for the ITS analysis. Given the large amount data (12 years before the intervention), the range of pre-intervention data will be restricted to ensure the validity of the comparison (i.e. historical trends might differ from the most recent ones). To analyse the impact of restrictions adopted in 2022, analysis will be conducted using data from 1st January 2021 onwards. For NOMAC, the intervention adopted in 2018 will be assessed using data from 1st January 2017 onwards. Methodological considerations will be evaluated based on the visual assessment of the trends. This may include adjustments on the amount of pre-intervention data or the frequency of data points, if deemed necessary to support the analysis.

Results will be reported overall and stratified by dose (high- vs. low- dose products) and indication (non-HRT vs. HRT).

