#### A. Primary analysis

Hypothesis:	Objective 1: Not applicable, descriptive analysis.
	Objective 2: Cumulative dose and duration of treatments with NOMAC or CMA will be lower after the implementation of restrictions.
	Objective 3: The number of new users of NOMAC or CMA with prior history of meningioma will be reduced after the implementation of restrictions.
	Objective 4: The number of users initiating NOMAC or CMA as first-line treatment will be reduced after the implementation of restrictions.
	Objective 5: The number of discontinuations and switches from NOMAC or CMA to other drug classes will increase after the implementation of restrictions.
	Objective 6: The incidence of NOMAC or CMA will be reduced after the implementation of restrictions, especially for high-dose products. This reduction will not be observed for other drug classes of interest.
Exposure contrast:	Objective 1: Not applicable, descriptive analysis.
	Objective 2: Pre-intervention (1-year period) vs. Post-intervention (1-year period)
	Objective 3 to 6: Pre-intervention vs. Post-intervention
Outcome:	Objective 1: Incidence rates and prevalence of drug classes of interest
	Objective 2: Cumulative dose and treatment duration of NOMAC or CMA.

Authors: [name], [name], [name], [name], [name]

Version: V4.0

Dissemination level: Public

	Objective 3: Number and characteristics of users of drug classes of interest.
	Objective 4: Line of treatment when initiating NOMAC or CMA.
	Objective 5: Diagnosis with meningioma during treatment. Discontinuations and switches
	from treatments with NOMAC or CMA to others.
	Objective 6: Incidence rates of NOMAC or CMA.
	Drug classes of interest, NOMAC and CMA will be assessed separately.
Analytic software:	R
Model(s):	Objective 1: Not applicable, descriptive analysis.
	Objective 2 to 5: Standardised mean differences.
	Objective 6: Segmented regression (Poisson models).
Confounding adjustment method	
	Stratification.
Missing data methods	
	The absence of a record for a condition or medication will be considered as the absence of the disease or use of the medication.
Subgroup Analyses	
	Objective 1: Age groups, indication, study period. For NOMAC or CMA only: dose, WHO ATC 5 th level (if counts allow). A subgroup analysis will be performed restricting the study population to individuals with a prior history of meningioma.
	Objective 2: Study population, indication, study period.
	Objective 3: Study period.

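### Twelve of the 22 pre-intervention months in the 2022 interrupted time series fall in 2021, which the protocol says may still carry COVID-19 effects, and neither a control series nor a later-start analysis is pre-specified

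*Protocol*

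**What the plan says.** Protocol section 8.8, Objective 6: "To analyse the impact of restrictions adopted in 2022, analysis will be conducted using data from" 1 January 2021 onwards. Section 8.6.3 sets the periods: "Preintervention: from start date to October 2022; Postintervention: from February 2023 to study end". It treats November 2022 to January 2023 as a transition: "For objective 6, aggregate monthly figures of this time period will be excluded".

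The model is a Poisson (or quasi-Poisson) segmented regression with a step and a slope change. On which series enter it, section 8.8 says "This analysis will be restricted to NOMAC and CMA (assessed separately"). Table 11 adds to the Objective 6 hypothesis that "This reduction will not be observed for other drug classes of interest", and lists stratification as the only method of confounding adjustment. The other classes receive monthly descriptive rates under Objective 1.

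Section 11 (Analysis) leaves out the 2020 action on NOMAC with oestradiol: "The rationale for this exclusion is that the 2020 intervention is likely to have been affected by the coronavirus disease (COVID-19) pandemic". It then says of the year used to start the series: "The effect of the COVID-19 pandemic might still be seen in 2021, which will affect the ability to capture stable trends for Objective 6".

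The stated safeguards are:
- visual assessment of the trends;
- permission to change the amount of pre-intervention data or the frequency of points if needed;
- linearity and autocorrelation checks, with the ITS not conducted if they fail.

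**The concern.** The pre-intervention slope is extrapolated past January 2023 to form the counterfactual. If prescribing was still recovering in 2021, the fitted slope is too steep, and flat prescribing in 2023 looks like a reduction. If early 2021 instead held a catch-up excess, the slope is too low and a real reduction is partly hidden. The Poisson interval reflects sampling error and does not include this error.

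A concurrent series would help to tell the two explanations apart. The protocol makes a prediction about other classes but specifies no model that tests it. Nor does it say in advance when the pre-period would be shortened, so that choice would be made after seeing the outcome series.

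**Working it through.** **1. Pre-intervention months.** January to December 2021 is 12 months; January to October 2022 is 10. Total 12 + 10 = 22, and 12/22 = 54.5% lie in 2021.

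**2. Post-intervention months at the Table 3 data locks.**
- Germany: lock 30-09-2023, less the six months that section 11 removes from the IQVIA databases, leaves February and March 2023 = 2.
- Belgium: lock 31-12-2023, less six months, leaves February to June 2023 = 5.
- Croatia (NAJS): lock 17-11-2023, last complete month October, leaves February to October 2023 = 9.

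**3. Model.** log E(Y) = b0 + b1·t + b2·post + b3·post·(t − 25). Here t = 0 is January 2021 and t = 25 is February 2023; t = 22 to 24 (the transition) are dropped. The step RR is exp(b2). The RR at the middle of the post segment is exp(b2 + b3·m), with m = 0.5, 2 or 4 months for 2, 5 or 9 post months.

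**4. Assumed disturbance.** The documents give none, so a range is used. With no true effect, the expected level is 1 − d(1 − t/12) for t < 12 and 1 afterwards. A negative d is an excess.

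**5. Noise-free fit.**

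| Assumed January 2021 level | Step RR | Mid-post RR, 2 / 5 / 9 months |
|---|---|---|
| 5% low | 0.978 | not tabulated |
| 10% low | 0.957 | 0.954 / 0.947 / 0.937 |
| 20% low | 0.913 | 0.908 / 0.893 / 0.874 |
| 10% high | 1.043 | not tabulated |

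In the 20% case the model predicts 1/0.913 = 1.095 for February 2023, when the true level is 1.

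Other shapes were also tried: recovery by June 2021, or a constant shift through 2021. The step RR is then 0.978 to 0.983 (5% deficit), 0.954 to 0.965 (10% deficit), 0.904 to 0.931 (20% deficit) and 1.035 to 1.043 (10% excess).

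**6. Would the checks catch it?** This was simulated with assumed monthly counts and a 5% quadratic test on the 22 pre-intervention months, standing in for the protocol's unnamed goodness-of-fit test.
- 100 to 200 incident users per month: a 10% dip is missed in about 88 to 90% of runs and a 20% dip in about 54 to 74%. With a Ljung-Box test added, both tests miss in about 78 to 82% and 49 to 67%.
- 300 per month, 20% dip: about 60% detected; a false significant step in 28 to 48% of runs.
- 500 to 1,000 per month, 10% dip: missed in 51 to 70%; a false significant reduction in 24 to 43%.
- 1,000 per month, 20% dip: detected in 98 to 99%.

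Detection and false-step percentages each count all runs; they are not joint.

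**7. Alternatives.** Starting in January 2022 leaves 10 pre-intervention months and gives a step RR of 1.000 in every scenario, because the assumed disturbance ends in December 2021. A control series with the same relative disturbance gives the same spurious RR, so the ratio is 1.000.

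**The case against.** A reader might infer that the plan will read pandemic recovery as an effect of the restrictions, with visual inspection as the only protection. The documents do not support that. The limitations section says an effect might be seen, and gives neither its direction nor its size. Section 8.8 allows the pre-period to be changed, and moving the start to January 2022 would remove the disturbance assumed here. Linearity is checked with goodness-of-fit tests as well as by eye, residual autocorrelation is examined, and failure of either cancels the ITS. Monthly rates for other classes would show a shared recovery descriptively.

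The noise-free figures also leave out sampling error and these checks. At 100 users per month, a 20% dip gives an expected step interval of about 0.73 to 1.14 (2 post months) to 0.78 to 1.07 (9), with false significant steps in 11 to 20% of runs. A 10% dip gives 7 to 9%, near nominal. With large counts a large dip is nearly always detected.

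All of this stands, and it limits the claim to a conditional one. It does not close the gap. A moderate dip often passes the checks. The freedom to change the pre-period has no stated rule. If the checks do fire, Objective 6 yields no estimate, because section 11 also calls ARIMA models infeasible.

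Two further points stand. The month counts of 2, 5 and 9 rest on the Table 3 locks; code execution is planned for March/April 2025, and Objective 2 plans a post-period to January 2024, so later data may be used. The step RRs do not depend on this. And the natural control class is a listed switch destination in Table 8 and need not share the same disturbance, so agreement with it should not be a condition for the conclusion.

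**Conclusion.** The point holds as a conditional weakness. More than half of the pre-intervention series lies in a year that the protocol itself doubts, and nothing fixed in advance separates a pandemic disturbance from an effect of the restrictions. Under the assumed disturbances the spurious step is about 2%, 4% or 9% downward for a 5%, 10% or 20% deficit, and about 4% upward for a 10% excess. These sizes illustrate the mechanism and do not estimate what happened. The bias matters little if the true effect is very large, and most for modest effects and moderate disturbances that the checks let through.

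**What to change.** In section 8.8, Objective 6, and in Table 11, pre-specify two additions.

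(a) Fit the same segmented model, over the same months, to the combination-product class with the NOMAC and CMA codes removed. Report the ratio of step RRs and of slope RRs beside the single-series RR, as a supporting analysis. This also tests the prediction about other classes. The code list already exists in Appendix I, so the cost is one more monthly series and one interaction model. It assumes a shared relative disturbance, and switching into the control class can inflate the apparent effect in the ratio.

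(b) Repeat the NOMAC and CMA analyses with the pre-period starting in January 2022, as a sensitivity analysis reported whatever the plots show. The cost is precision: 10 pre-intervention months instead of 22.

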# 12. MANAGEMENT AND REPORTING OF ADVERSE EVENTS/ADVERSE REACTIONS

Adverse events/adverse reactions will not be collected or analysed as part of this evaluation. The nature of this non-interventional evaluation, through the use of secondary data, does not fulfil the criteria for reporting adverse events, according to module VI, VI.C.1.2.1.2 of the Good Pharmacovigilance Practices (https://www.ema.europa.eu/en/documents/regulatory-procedural-guideline/guideline-good-pharmacovigilance-practices-gvp-module-vi-collection-management-submission-reports en.pdf).

Only in case of prospective data collection, there is a need to describe the procedures for the collection, management and reporting of individual cases of adverse events/adverse reactions.

#### 13. GOVERNANCE BOARD ASPECTS

All data sources (except for IQVIA DA Germany and IQVIA LPD Belgium) require approval from their respective governance boards.

# 14. PLANS FOR DISSEMINATING AND COMMUNICATING STUDY RESULTS

A study report including an executive summary, and the specified tables and/or figures will be submitted to EMA by the DARWIN EU® CC upon completion of the study. An interactive dashboard incorporating all the results (tables and figures) will be provided alongside the study report. The full set of underlying aggregated data used in the dashboard will also be made available if requested.

#### 15. OTHER ASPECTS

Not applicable.

# 17. ANNEXES

**Appendix I**: List with preliminary concept definitions.

# **Meningioma:**

Concept ID	Concept Name
4250780	Angiomatous meningioma
4029200	Atypical meningioma
609195	Atypical meningioma of cerebral meninges
4260192	Benign meningeal neoplasm
37110097	Benign meningioma
608204	Benign meningioma
376063	Benign neoplasm of cerebral meninges
4003171	Benign neoplasm of meninges
135767	Benign neoplasm of spinal meninges
4130540	Cerebellopontine angle meningioma
4098901	Cerebral meningioma
4212098	Clear cell meningioma
4300672	Cutaneous meningioma
35622955	Familial multiple benign meningioma
4176436	Fibrous meningioma
4261967	Hemangioblastic meningioma
4118992	Intracranial meningioma
4102396	Lymphoplasmocyte-rich meningioma
4189335	Malignant meningeal neoplasm
37017114	Malignant meningioma of meninges of brain
4112969	Malignant meningioma of optic nerve sheath
4177240	Malignant tumor of meninges
4133829	Meningeal neoplasm (morphology)
763799	Meningioma of cerebellum
4114200	Meningioma of optic nerve sheath
4186247	Meningioma of orbit
608281	Meningioma of uncertain behavior
608280	Meningioma uncertain whether benign or malignant

Authors: [name], [name], [name], [name], [name]

Version: V4.0

Dissemination level: Public

4266488 Meningioma, chordoid 4301120 Meningioma, malignant 4164328 Meningioma, rhabdoid 4164954 Meningiomatosis 4288742 Meningothelial meningioma	
4164328 Meningioma, rhabdoid 4164954 Meningiomatosis	
4164954 Meningiomatosis	
, , ,	
4288742 Meningothelial meningioma	
Weimigothera memigiona	
608205 Metaplastic meningioma	
4099822 Microcystic meningioma	
4130542 Neoplasm of cerebral meninges	
4131105 Neoplasm of meninges	
4130041 Neoplasm of spinal meninges	
4314637 Neoplasm of uncertain behavior of cerebra	l meninges
438997 Neoplasm of uncertain behavior of mening	es
4317020 Neoplasm of uncertain behavior of spinal m	neninges
4030268 Papillary meningioma	
36716634 Primary malignant meningioma	
436926 Primary malignant neoplasm of cerebral mo	eninges
4002340 Primary malignant neoplasm of meninges	
134295 Primary malignant neoplasm of spinal men	inges
4303729 Primary optic nerve sheath meningioma	
4243303 Psammomatous meningioma	
4303730 Secondary optic nerve sheath meningioma	
4100554 Secretory meningioma	
4098902 Spinal meningioma	
4277603 Transitional meningioma	
4175395 Xanthomatous meningioma	

